The analysis shows a trend towards faster healing in the areas treated with EmoLED compared to the untreated ones: considering the healing time and the post-operative course it seems significantly faster for the areas treated with EmoLED compared to those treated only with standard dressings. The third multicenter study was performed on chronic leg ulcers with a wound presence of at least 8 weeks. The study involved the enrollment of 90 patients who have two wounds, one of which was used as a control wound, or had only one particularly large wound, which is only half treated with EmoLED. Enrolled patients were followed up on an outpatient basis for 10 weeks. The results significantly demonstrate that wounds or parts of wounds treated with EmoLED had a higher mean re-epithelialization at week 10 than wounds treated with standard dressings only. The 10 week healing trend is also significantly higher in wounds treated with EmoLED. The pain trend measured with the VASS scale undergoes a significant reduction already starting from the fourth week of treatment. The study shows in particular the efficacy of the device under study in venous type ulcers. A further multicenter clinical study is currently underway with the EmoLED device which plans to observe patients with venous or mixed wounds over a period of 16 weeks. This trial is aimed not only at demonstrating therapeutic efficacy and safety, but also improving the quality of life of patients and the cost / benefit ratio for society and for health.

In this study are compared the control group -of patients who go to the clinic twice a week- and the treated group -of patients treated with EmoLED who visit once a week receiving blue light application in addition to standard treatment-. In this case, no data are yet available as enrollment is at 30% and only a small number of patients completed the study. However, no expected or unexpected side effects or device-related adverse events were found.

In conclusion, since no adverse event or side effect have been recorded and since the wounds treated with EmoLED healed faster and better than the control wounds, the risk-benefit ratio is assessed clearly shifted towards the benefit.

Study Objectives

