The deadline for the above reports is commensurate with the seriousness of the serious accident and in accordance with the prescriptions ascribable to Article 87 of the European Regulation. This timing is to be understood starting from the moment in which a connection, even potential, is established between the accident and an EMOLED brand device.

The timing is as follows:

- a) Manufacturers report any serious accident immediately after establishing the causal link, even if only reasonably possible, between the accident and their device, and no later than 15 days after becoming aware of the accident;
- b) In case of a serious threat to public health, the manufacturer sends the report immediately and no later than 2 days after becoming aware of the threat;
- c) In the event of death or an unexpected serious deterioration in the health of a person, the report is transmitted immediately after the manufacturer has ascertained or as soon as it assumes that there is a causal link between the device and the serious accident and in any case within 10 days after the date on which the manufacturer becomes aware of the serious accident.

To ensure timely reports, in accordance with the provisions of the applicable legislation, EMOLED may, if necessary, adopt the policy of submitting incomplete initial reports, but within the prescribed time frame, making use of the possibility of completing and possibly correcting the information initially forwarded with the following forwarding of complete final report. If, after becoming aware of an accident potentially to be reported, there still is uncertainty about the need to report the accident, the manufacturer in any case sends a report within the prescribed time frame as defined above.

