Early termination and suspension of clinical evaluation

In the event of suspension or early termination of the study by the promoter, taken as a safety measure due to events related to the conduct of the study that may affect the health of the patients recruited, the promoter is required to notify the Ministry of Health and the Ethics Committees involved within 90 days from the recruitment of the last patient or the early closure. In case of suspension or early termination of the study not for safety reasons, the sponsor shall justify and explain their decision. The suspended clinical trial cannot be reactivated unless a substantive amendment and the positive opinion of the Ministry of Health and the Ethics Committees have been submitted.

Statistics

Calculation of the sample number

Lack of reliable data in the scientific literature on average recovery times of decubitus ulcers (PUs), the absence of clinical experience combining blue light treatments with the therapy of this type of lesion, and the lack of reliability about any inference based on clinical studies that associate this type of treatment with other types of skin lesions, due to the different aetiologies and types of patients, do not make possible to perform a reliable calculation of the sample number. The predefined sample size was therefore set on the basis of considerations concerning the recruitment capacity of the centre involved in the project. Based on an estimate of the historical clinical activity data at the Cardiorespiratory Rehabilitation Units, at the Neuro-Motor Rehabilitation Unit and at the Acquired Severe Brain Injury Unit (UGCA), where patients will be enrolled, the percentage of patients with decubitus ulcers at the entrance is about 20%, an information that implies that compared to an average of about 426 patients/ year, in 10 months of enrollment it is possible to reach a number of 40 patients compared to a percentage of drop-out/ waste equal to about 25%. A total of 40 patients will be recruited, 20 patients with second stage PUs and 20 patients with third stage PUs. Thus, this study is intended as a "proof of concept", the results of which may be used as preliminary information to define the sample size in later studies.

Management of missing data

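### Notice of a safety-driven suspension or early termination may reach the Ministry and the Ethics Committees up to 90 days later, from either of two start dates and with none fixed for a suspension

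*Combined protocol and SAP*

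**What the plan says.** The rule is in the section Early termination and suspension of clinical evaluation. It opens with its trigger: "In the event of suspension or early termination of the study by the promoter, taken as a safety measure", because of study-related events that may affect the health of recruited patients. In that case "the promoter is required to notify the Ministry of Health and the Ethics Committees involved", and the time allowed is "within 90 days from the recruitment of the last patient or the early closure". For stops without a safety reason the section asks the sponsor to justify the decision and sets no time limit. A suspended trial may restart only after a substantive amendment and positive opinions from the Ministry and the Ethics Committees.

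The section Timing for reporting sets the manufacturer's limits for serious accidents. The general limit is "no later than 15 days after becoming aware of the accident". For a serious threat to public health it is "no later than 2 days after becoming aware of the threat". For a death or an unexpected serious deterioration it is 10 days from awareness. The section Reporting by the manufacturer to the Ministry of Health sends these reports to the competent authorities.

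**The concern.** A stop made for safety is when outside oversight is most needed, yet the only time limit that the protocol sets for announcing such a stop is about three months. The start of that period is also unclear. Recruitment of the last patient says nothing about when a safety decision was taken. Early closure fits a termination but not a suspension, which closes nothing.

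The Ethics Committees have most at stake. They must give a positive opinion before a suspended study restarts, and under the section on amendments they approve any substantive change. The plan still lets them learn of the stop up to 90 days after it happened. Nothing here affects the sample size, the significance level or the analysis.

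**Working it through.** The 90 days is a procedural limit with no formula behind it, so there is no figure to reproduce. The check is a comparison of the rules, with simple arithmetic.

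**Step 1. The duties side by side.**

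| Duty | Trigger | Recipient named | Limit | Clock starts |
|---|---|---|---|---|
| Notice of a stop (Early termination and suspension) | Safety stop for study-related events that may affect patients' health | Ministry and Ethics Committees | 90 days | Last recruitment, or early closure |
| Vigilance report (Timing for reporting, item a) | Any serious accident | Competent authorities | 15 days | Awareness |
| Same section, item c | Death or unexpected serious deterioration | Competent authorities | 10 days | Awareness |
| Same section, item b | Serious threat to public health | Competent authorities | 2 days | Awareness |

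**Step 2. Latest permitted notice, in days after the stop.**
- Clock from early closure (termination): 90 days.
- Clock from last recruitment, with the stop *s* days later: 90 − *s*. If the last recruited patient is still in the 4-week (28-day) observation period, *s* runs from 0 to 28. The result runs from 90 − 0 = 90 down to 90 − 28 = 62 days.
- Suspension: no closure has occurred, so only the recruitment date is left, and it is not tied to the decision.

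**Step 3. Distance from the plan's other limits.** 90 − 15 = 75 days, 90 − 10 = 80 days and 90 − 2 = 88 days. As ratios, 90/15 = 6, 90/10 = 9 and 90/2 = 45. These figures compare the urgency of two different duties. They do not measure a delay in reporting an accident.

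**Step 4. What the vigilance rules leave uncovered.**
- *Recipients.* The sections on reporting by health professionals and by the manufacturer, on timing and on reporting criteria name the Ministry, the competent authorities and the manufacturer. None names the Ethics Committees.
- *Scope.* Reporting incidents criteria requires an event, a suspected device contribution, and actual or possible death or serious deterioration. The trigger for a safety stop is wider. A stop for an event that fails any of these criteria is covered only by the 90-day rule, for the Ministry as well as for the Ethics Committees.

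**The case against.** The strongest reply is that the two sets of limits govern different duties and run in parallel. The section Accidents and their reporting says that market surveillance rules apply even though the device is used in a study. A serious accident behind a stop would therefore still reach the authority in 2, 10 or 15 days, and health professionals must notify the Ministry and the manufacturer at once. The study has already stopped, restart is barred without positive opinions, and the consent section has patients told of news as soon as the investigator receives it. The protocol also binds the study to local law, which is not reproduced and may be stricter.

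All of this stands for serious accidents and for the Ministry. It does not reach the two gaps in step 4, and a general reference to local law does not cure an explicit 90-day rule.

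A reader might infer more than the text supports:
- *The clock runs only from an unrelated date.* It does not. For a termination, early closure is the stop.
- *The 90 days contradicts the 2 to 15 days.* It is a mismatch in urgency between parallel duties.
- *Accident reports can also be late, because "This timing is to be understood starting from the moment in which a connection, even potential, is established between the accident" appears beside limits counted from awareness.* The opening sentence is loose, but items a to c each set an outer limit from awareness. A potential link is enough, and a report is due on time even when the need for it is uncertain.
- *Notice of a suspension could be put off past 90 days by later recruitment.* Restart needs the opinions of the same bodies, so this is unlikely in practice.
- *Further patients would be treated during the 90 days.* Not in this study, which has stopped.
- *Patients elsewhere are exposed, since "A further multicenter clinical study is currently underway with the EmoLED device".* That study's notification rules are not in these documents, so this is speculation.

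**Conclusion.** The point holds as a gap in oversight. A safety stop may be announced to the Ministry and the Ethics Committees up to 90 days after it, with no rule for choosing between the two start dates and none specific to a suspension. The documents contain no shorter route to the Ethics Committees. For events below the serious-accident threshold they contain no shorter route to the Ministry either.

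The range of 62 to 90 days under the recruitment date assumes that the stop falls while the last recruited patient is under observation. The conclusion rests on the protocol text alone and assumes that no document outside it sets a shorter limit. The point should be corrected before the study runs, because a stated rule that permits late notice is worse than a missing detail.

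**What to change.** In Early termination and suspension of clinical evaluation, for safety-driven stops only:
- remove the 90-day limit and the start date tied to the last patient's recruitment;
- name suspension explicitly alongside termination;
- count from the date of the decision to suspend or terminate;
- require prompt notice to the Ministry and the Ethics Committees, no later than 15 days, which is the longest limit the plan already uses for serious accidents, or sooner where the 2-day or 10-day limit applies to the triggering event.

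The 15-day ceiling also covers stops prompted by events that fall in none of the serious-accident classes. The latest permitted notice after a termination then falls from 90 to at most 15 days.

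Stops without a safety reason have no time limit now, and this change need not create one. Timing for reporting can stay as it is. The cost is a sentence or two of protocol wording. The rule concerns notification only and does not alter when treatment or the study is stopped.

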Furthermore, through the action on the T lymphocytes present in the wound bed, ROS are able to promote the phenotypic transition of macrophages from M1 (pro-inflammatory) to M2 (pro-healing) (15, 16). This combination of effects suggests a positive action on the inflammatory stasis that characterizes some types of "non-healing" wounds: an increase in inflammation such as to induce the body to a consistent response and the consequent stimulation for the following phases.

Through the production of HIF-1 α (Hypoxia-inducible factor 1-alpha) and the consequent release of proangiogenic factors and induction of eNOS (endothelial Nitric Oxide Synthase) ROS also play a role in promoting angiogenesis (17, 18) and therefore in the increase of the nutrient and oxygen supply in the wound bed, of great importance in the proliferation phase.

The device has been designed and set to deliver a power density of about 7 J/cm² in an acceptable treatment time for both doctor and patient (60 seconds).

[figure not shown]
The choice of the duration of the treatment was also made on the basis of what is stated in literature on thermal damage: the treatment induces a temperature between 45 and 50 °C in the treated area, ideal condition to stimulate the reversible and physiological phenomena that we want to induce.

Table 3.6. Thermal effects of laser radiation

Temperature	Biological effect
37°C	Normal
45°C	Hyperthermia
50°C	Reduction in enzyme activity, Cell immobility
60°C	Denaturation of proteins and collagen, Coagulation
80°C	Permeabilization of membranes
100°C	Vaporization, Thermal decomposition (ablation)
> 150°C	Carbonization
> 300°C	Melting

The physiological phenomena induced by temperature (11)

The same volume shows a curve that links the duration of the thermal stimulus with the reversibility of the process induced by this stimulus.

Critical temperatures for the occurrence of cell necrosis in relation to the duration of exposure (11).

This data on the physiological effects of temperature was the first constraint for the definition of treatment parameters.

In addition to studies related to the influence of temperature, the decision of treatment time is based on a finite element model (11) which correlates optical power, treatment time and final temperature induced by the treatment with the device in question. The initial model led to establish the conditions of optimal work, that were then tested in an animal model study.

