2. Safety of treatment (number of related adverse events in the two groups).

Measurable parameters

After enrolment and signature of the informed consent, the salient data, in the appropriate case report form, and the photographic images of the 2° and 3° stage injuries of each patient will be collected.

Three times a week (in conjunction with the dressing change) data, on patient forms, will be recorded, while once a week and at the last visit, if healing has not occurred before, the photographic images of each lesion of 2° and 3° stage will be captured.

All these variables will be measured during the 4-week observation period. The date of recovery, if it occurs before the end of the observation period, will be recorded in the patient’s case report form and the photographic image of the healed area will be acquired.

WEEK	W 1			W 2			W 3			W 4		
VISIT	V 1	V 2	V 3	V 4	V 5	V 6	V 7	V 8	V 9	V 10	V 11	V 12
CRF	P	P	P	P	P	P	P	P	P	P	P	P
PICTURE	P			P			P			P		P

Recording of clinical data

Data related to the evaluation of the endpoints are acquired during the visit for both study groups and will be inserted in pseudonymized form within a computerized database, where each subject will be associated with an alphanumeric identification code. The key of patient association code will be kept by the Principal Investigator for the duration of the study, it will not be communicated to the Sponsor and to the scientific coordinator and it will be eliminated at the end of the study, making the data completely anonymous.

The parameters of the Case Report Form and the photographic images of the lesions are both acquired and stored in digital format, during the length of the clinical trial and afterwards, for 10 years after the conclusion of the study.

Once the storage period indicated above has expired, the data will be anonymized so that it is no longer possible to trace, directly or indirectly, the identity of the interested subject. Anonymized data may be reused for further research and may therefore be stored indefinitely.

Each photograph of the lesions will be identified only with the patient code and the date of the visit.

The analysis of the photographic images will be performed through an appropriate analysis algorithm that measures in mm² the surface of the lesion.

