If the patient has two or more decubitus lesions at the same stage, the doctor will choose to treat the lesion of which, in his opinion, the data acquisition (photography and size measurement) is better. If a patient has two or more lesions of different stages, the doctor will decide to include in the study only one of them, based on the number of lesions inserted at that time in the two groups, choosing the group with a smaller number: In this way, attempts are made to ensure a numerical trend as simultaneous as possible in the two groups of lesions (e.g. if the number of 2°stage lesions enlisted is less than the number of 3°stage lesions enlisted, then the 2°stage lesion will be included in the study). In the case of a numerical parity of the two groups of lesions, the doctor will decide to treat the lesion with a position that allows a better data acquisition (photographic image, measurement, etc.).

Case Report Forms

Case Report Forms are unique to every patient. It will be used the form of injury assessment already present at the Investigator Centre; the data collection by the Principal Investigator includes: patient's name and surname, date of birth, room number, medical record number, date of surgery, any allergies and the characteristics of the lesion under investigation -position and degree of the lesion-. Another section dedicated to the characteristics of the lesion, includes: dimensions (length x width), the amount of exudate and the type of tissue. All these features will be evaluated, according to the criteria of the international scale PUSH, with a score, specified in the legend in the form, of which the total will be reported at each visit.

The Pressure Ulcer Scale for Healing (PUSH) is a tool designed by the National Pressure Ulcer

Advisory Panel (NPUAP) and used to observe the trend of pressure ulcers over time, classifying them regarding the area of extension, the exudate and the tissue type, noting the partial score for each characteristic of the ulcer and summing those scores to obtain the total. Comparing the relevant total scores over time will provide an indication of the improvement or worsening of the healing of the pressure ulcer.

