The standard treatment for 2° and 3° stage PU consists of: cleansing with saline or ringer's lactate, hyaluronic acid gauze plus polyurethane foam every 48 hours or as needed. In addition, zinc cream or hyaluronic acid sodium salt + metallic silver is applied to prevent and/or treat the skin maceration of the surrounding area, and eventual debridement of the lesion, application of topical treatment indicated for that stage of the lesion (as provided by the "Protocol on pressure ulcers' dressing" intended as the "standard of care" of the structure) and subsequent bandage (that generally consists of a polyurethane film -thin hydrocolloid plate or a pressure discharge system made with hydrocolloids and polyurethane foam, known as "pressure relief system"), are planned.

During the 4 weeks of treatment with the EmoLED device or until healing, treatments with other types of phototherapy (including photodynamic therapies), topical negative pressure therapy or additional skin grafts are not allowed.

If, during the 4 weeks of observation, clinical signs of infection occur, a Silver dressing will be preferably applied. In any case, each participating site is left free to choose the most suitable dressing among those available to the structure, as long as the same dressing is adopted both in the Control Group and in the Treated Group.

If at the conclusion of the patients' participation in the clinical investigation, any additional treatments to those normally provided for the clinical condition considered in this study, caused by the participation itself in this trial, are necessary, the Sponsor will bear the costs incurred for such treatments.

Known or predictable factors that may compromise the results and their interpretation

An incorrect recording of photographic images does not make it possible to determine the area of the lesion via software. This problem is tackled by providing precise instructions on the correct use of the tools available for the retrieval of images.

Poor management of bedridden patient placement may affect the reliability of the result. This problem is contained by well explaining to the involved staff the importance of the adherence to the protocols of the structure regarding the positioning of patients, and including in the trial only suitably trained and experienced personnel in the management of the bedridden patient.

Subjects discontinuation and withdrawal from the clinical investigation

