Since it is a "proof of concept" study based on a limited number of patients, we will include in the study also patients who do not conclude the study according to the principle "intention to treat" and the resulting missing data will be processed through the imputation technique of the missing data *last observation carried forward - LOCF*. If the patient does not leave the study but skips one or more visits, the averages of the two adjacent visits or the last available data (LOCF) will be taken into account.

Statistical analysis

Demographic and clinical data will be presented in tables and graphs in the form of frequencies and percentages for categorical variables, mean, standard deviation, median and interquartile range for continuous variables, differentiating by reference population and treatment group. At a first analysis a qualitative comparison will be carried out between the treatment groups (improvement or not improvement), both general and differentiated for lesion of 2° and 3° stage, through the χ^2 test or Fisher's exact test for counts of less than 5. The results will be presented in contingency tables and bar charts.

A quantitative comparative statistic between the treatment groups will then be performed by comparing the outcome variables (percentage reduction of the lesion area and reduction of the PUSH index) through the non parametric test of Mann-Whitney, one of the most powerful nonparametric tests used to verify whether two independent groups belong to the same population. The Mann-Whitney test is usually applied when the assumptions to perform the parametric test are not met, which means when the distribution of the variable under study is not normal and/or the sample sizes are reduced (n 30 cases in at least one sample).

In this case, the choice to perform a non parametric analysis lies in the low sample size and therefore it is preferred to have more conservative meaningfulness values. The results will be presented in tables, with median and interquartile interval in the two groups with the relative p. value, and graphically, through box plot.

To analyse the internal and between groups time-related differences, Friedman's non-parametric test for the outcome variables will be performed.

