Generalized linear models (GLM) will be used to investigate whether differences between the two groups are influenced in a confounding way by demographic and clinical covariates, pre-treatment measurement, and to measure their impact that will allow us to understand which variables affect the outcome and will also allow us to analyse the differences between groups being equal for these covariates.

A descriptive statistic of adverse events, if present, will also be made through tables with frequencies and percentages, and bar charts.

All significance tests will have a statistically significant p. value <0.05. The analysis will be carried out with the open source software R Commander (v. 2.2-0).

croData publication policy

At the end of the clinical study and of the related analysis about the obtained results, these will be made available anonymously and aggregated in full respect of the protection of the right to privacy, in accordance with Regulation no. 2016/679 (GDPR, General Data Protection Regulation), for publication in national or international journals, or for presentation by investigators at scientific conferences and in medical journals. For the writing of any publications concerning the study in question, may be used professional medical writers who will write manuscripts on behalf of the company and for which the company undertakes to ensure analogous compliance with current legislation.

After the conclusion of the study, the sponsor will be responsible for drawing up the final report of the clinical trial in the manner and timing prescribed in the current legislation regarding clinical investigations; external consultants of the sponsor, experts in this field, may be involved in the preparation of the final report and for which the sponsor ensure the same compliance with current legislation.

References

1. Clark R (1985) Cutaneous tissue repair: basic biological considerations. *J Am Acad Dermatol* 13: 701-725.
3. Nwomeh BCM Yager DR, Cohen IK (1998) Physiology of the chronic wound. *Clinics in Plastic Surgery* 25 (3): 341
4. Hackam DJ, Ford HR (2002) Cellular, biochemical and clinical aspects of wound healing. *Surgical Infections* 3: S23-S35.
5. Calderhead (2007), The photobiological basis behind light-emitting diode (LED) phototherapy, *Laser therapy*.

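### Worsening of the study ulcer can be derived from PUSH at every visit but is not counted by arm in any planned output; infection of the study ulcer has neither a visit field nor an analysis

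*Combined protocol and SAP*

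**What the plan says.** **Outcome comparison.** The first comparison in Statistical analysis has two classes: "At a first analysis a qualitative comparison will be carried out between the treatment groups (improvement or not improvement". It is run overall and by stage, with a chi-square "test or Fisher's exact test for counts of less than 5", and is shown in contingency tables and bar charts. The variable and cut-off that define improvement are not given. PUSH reduction and percentage area reduction are then compared by Mann-Whitney and reported as medians, interquartile intervals, p values and box plots. Friedman tests cover change over time.

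**Safety.** The second secondary endpoint is "Safety of treatment (number of related adverse events in the two groups". The planned analysis is: "A descriptive statistic of adverse events, if present, will also be made through tables with frequencies and percentages, and bar charts".

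**What is recorded.** Visits take place three times a week for 4 weeks. The Case Report Forms section says that the Patient Visit form holds the PUSH items, the dressings and any notes. On the PUSH total it says: "Comparing the relevant total scores over time will provide an indication of the improvement or worsening of the healing of the pressure ulcer". Photographs, the source of the software-measured area, are scheduled at V1, V4, V7, V10 and V12 only.

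**Infection.** The section on procedures and follow-up foresees it: "If, during the 4 weeks of observation, clinical signs of infection occur, a Silver dressing will be preferably applied". The site otherwise stays free to choose its dressing. Infection is not among the listed visit fields.

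**Masking.** The Bias section says that allocation cannot be masked.

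**The concern.** The stated objective covers both effectiveness and safety in supporting repair of the ulcer. Deterioration of the irradiated ulcer is the harm closest to that objective. The protocol recognises that serial PUSH totals can show it, yet the analysis has no place where it is counted.

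Three features combine:

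- The two-class table cannot separate worsened from unchanged lesions.
- The safety endpoint depends on a judgement of relatedness made by unmasked staff. The protocol defines accidents and serious accidents but not adverse events, so a rise in PUSH or an infected study ulcer need not be logged as one.
- Infection has no field of its own and no analysis.

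The protocol's account of how the device works gives a reason to look. It describes "an increase in inflammation such as to induce the body to a consistent response and the consequent stimulation for the following phases". It also states, in the sample-size section, that there is no clinical experience of blue light in this type of lesion. A report that follows the plan could give equal improvement rates and no related events, and conclude that the treatment is safe, without stating how many study ulcers got worse in each arm.

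**Working it through.** There is no plan figure to reproduce: the sample size was set by recruitment capacity, without a power calculation. The check has a textual part and an illustration.

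**1. Which planned output would show each outcome**

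| Planned output | Ulcer worsening | Infection of study ulcer |
|---|---|---|
| Improved / not improved table | Merged with unchanged | Not shown |
| Mann-Whitney, interquartile interval, box plot | Indirectly, as negative reductions | Not shown |
| Friedman test over time | Indirectly, no count | Not shown |
| Related adverse events (endpoint) | Only if logged and judged related | Only if logged and judged related |
| Adverse-event tables (analysis) | Only if logged | Only if logged |

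No row gives a count of worsened lesions by arm.

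**2. Effect of the merge**

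Inputs: 20 per arm (from 10 per arm within each stage). Assumed: 14 improved in each arm; the other 6 are all unchanged on control, while w of them worsened on EmoLED.

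- Planned table: 14/20 v 14/20, Fisher p = 1.00 for every w from 0 to 6.
- Worsening tabulated on its own, Fisher p: 3 v 0, 0.231; 4 v 0, 0.106; 5 v 0, 0.047; 6 v 0, 0.020.

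**3. Would the quantitative summary reveal it?**

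Assumed PUSH reductions: improved +3, unchanged 0, worsened -3. With n = 20 and the usual (R default) quartile, the lower quartile lies at position 1 + 0.25 × 19 = 5.75, that is, the 5th lowest value plus 0.75 × (6th - 5th).

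| w on EmoLED | 5th, 6th lowest | Lower quartile | Median | Upper quartile |
|---|---|---|---|---|
| 0 to 4 | 0, 0 | 0 | 3 | 3 |
| 5 | -3, 0 | -3 + 0.75 × 3 = -0.75 | 3 | 3 |
| 6 | -3, -3 | -3 | 3 | 3 |

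Up to 4/20 = 20% worsened, the tabulated summary is identical to no worsening at all. From the fifth, the lower quartile moves. The threshold depends on there being 14 improved and 6 not improved, not on the size of the gains. With more varied gains among the improved (2 to 8 points) and 6 v 0 worsened, the medians are equal (3 v 3), Mann-Whitney p = 0.63, and the lower quartiles are -3 v 0.

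**4. What a direct count can support**

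- Exact 95% intervals at n = 20: 2/20 = 10% (1.2% to 31.7%); 5/20 = 25% (8.7% to 49.1%).
- If none worsened, the one-sided 95% upper limit is 1 - 0.05^(1/20) = 13.9%.
- Power of Fisher's test at 20 per arm: 24% for 30% v 10%; 49% for 40% v 10%.

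A described count with an interval is therefore realistic; a formal test is not.

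**The case against.** The strongest reply is that worsening is not lost. The two-class comparison is only a first analysis. The primary endpoint is PUSH reduction, where a worsened lesion enters as a negative value, and interquartile intervals, box plots and tests over time are planned. This largely stands: with five or six worsened lesions in the example the lower quartile falls below zero, and with fewer they would still appear as a whisker or outlying points on the plot. A reader might infer that harm to the ulcer would go unreported altogether; the documents do not support that. What remains is that no count, definition or interval is planned.

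Second, the adverse-event tables in the analysis section are not limited to related events; only the endpoint is. That is correct, and an infection or deterioration logged as an adverse event would appear there. Nothing requires the logging.

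Third, a reader might infer that infection data are already collected and merely left out of the analysis, with the silver dressing as a marker. They are not. Infection is not a listed field, silver is only preferred when signs occur, and a product containing silver is also listed in routine care of the surrounding skin. Dressing type cannot stand in for infection.

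Fourth, the inflammation argument should not be pressed. The animal section reports more infiltrate in treated wounds in the first hours, but the reverse at 24 hours, and comparable macrophage populations at 18 and 24 hours. The mechanism is a reason to count worsening, not evidence of harm.

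Finally, this is a proof-of-concept study of 40 patients. That limits what any comparison can show, but it does not argue against a descriptive row in a table.

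**Conclusion.** The point holds as a gap in reporting, and correcting it is a cheap improvement. Worsening of the study ulcer can be derived from data collected at every visit, but no planned output counts it by arm; it would be visible only indirectly. Infection of the study ulcer is foreseen but has neither a listed field nor a planned analysis.

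The size is illustrative. With 20 per arm and 14 improved, as many as 4 worsened lesions leave the median and quartiles untouched, and the improvement table gives p = 1.00 even at 6 v 0. These counts and PUSH changes are assumptions, since the documents give no worsening or infection rates. The textual finding does not depend on them.

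**What to change.** 1. **Statistical analysis.** Keep the planned improvement test. Add a descriptive table of improved, unchanged and worsened lesions by arm, overall and by stage, from the week-4 PUSH total against baseline. Name the baseline visit, because the secondary endpoint refers to V0 while the visit schedule starts at V1.
2. **Secondary endpoints and adverse-event analysis.** For all randomised patients, by arm and whatever the relatedness, report the number with a PUSH total above baseline at week 4 and the number with it above baseline at two consecutive visits. Give exact 95% confidence intervals and no formal test. If area is also used, restrict it to the scheduled photograph visits and set a measurement-error margin in advance.
3. **Patient Visit form.** Add a yes/no item for signs of infection of the study lesion and tabulate it by arm. Do not infer infection from the dressing used.

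Cost: a few sentences, one table and one form item. A PUSH rise can reflect debridement or measurement noise; the two-visit count limits this, but the week-4 count does not. The intervals will be wide at 20 per arm. No clinical rule or dressing choice is proposed.
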